- Note that older subjects or those with significant comorbidities may be at higher risk of decompensation in this situation. When reactions occur in these vulnerable subjects, or in the case of rapidly progressing reactions, consider treatment with tocilizumab 8 mg/kg IV over 1 hour, with or without additional dexamethasone 10 to 20 mg IV (or equivalent).

Grade 3 and 4

- Stop the infusion and disconnect the infusion tubing from the subject.
- Administer additional dexamethasone 10 mg intravenously.
- Immediately give aggressive supportive care. Use pressors, fluids, oxygen, epinephrine or bronchodilators, ventilatory support, antipyretics, and analgesics as indicated.
- Treatment with tocilizumab, 8 mg/kg IV over 1 hour ([Hallek, 2018](#)), is encouraged for CRS due to the high risk of progression and permanent organ dysfunction.
- Hospital admission for observations is almost always indicated, usually to an intensive care unit, since an initial appearance of improvement may quickly yield to rapid decompensation.
- Subjects with Grade 3 CRS or infusion reaction may be rechallenged once resolved as described in [Section 4.7](#) and [Table 8](#). Subjects with recurrent Grade 3 or any Grade 4 reaction should not receive further plamotamab treatment but will continue to be followed on the protocol (ie, followed for long-term survival).
- Obtain an unscheduled blood sample for cytokine analysis during the event and approximately 4 hours later, unless scheduled cytokine monitoring is already in progress on the same visit day.
- Obtain an unscheduled sample for anti-drug antibodies (ADA) testing as close to the onset of the event as possible, at the resolution of the event, and approximately 28 days

following the event, unless scheduled cytokine monitoring is already in progress on the same visit day.

- Notify the Xencor Medical Monitor immediately.

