Table 10: Sampling for Plamotamab Anti-Drug Antibodies, Cytokines, PK, and ECGs, and Rituximab Levels

Plamotamab PK, cytokines, and ADA, as well as ECGs, are performed for subjects in Part 1 and subjects randomized to Arm A in Part 2. All times are relative to the plamotamab infusion. On days when tafasitamab and plamotamab are administered, draw predose samples and perform ECG before the start of the tafasitamab infusion.

Study Day	Pretreatment	Cycle 1				Cycle 2		Cycle 3		Cycle 4+	Post-treatment	
	-1	1	8	15	22	1	15	1	15	1	EOT	30d ±3 post EOT
Predose	Rituximab level	pPK, Cyto, pADA ECG ^a	pPK, Cyto,	pPK, Cyto	pPK, Cyto,	pPK Cyto, pADA ECG Rituximab level	Cyto	pPK Cyto, pADA ECG	Cyto,	pPK ^b pADA ^b ECG ^b Rituximab level ^h		
During the Infusion		pPK ^c ECG ^c		pPK ^d ECG ^d								
At the end of the infusion (+/- 10 min)		pPK ECG	ECG		ECG	pPK ECG	ECG	pPK ECG		pPK ^b ECG		
7 hr post infusion (+/- 30 min)		Cyto	Cyto	Cyto	Cyto	Cyto	Cyto ^g	Cyto ^g	Cyto ^g			
24 hr post infusion (+/-2 hr)		Cyto	pPK ^c Cyto	Cyto	Cyto	Cyto	Cyto	Cyto	Cyto			
48 hr post infusion (Day 3)		pPK ^f										
Post-treatment; not timed											pPK pADA	pPK pADA

Cyto = cytokine assays; d = day; ECG = electrocardiogram; EOT = end of treatment; pADA = plamotamab anti-drug antibodies; pPK=plamotamab pharmacokinetics.

^a ECG in triplicate: obtain three ECGs each separated by 2 minutes on Day 1 only; other ECGs are single studies.

^b In all even numbered cycles only

^c 1 hour (±10 minutes) after the start of Day 1 plamotamab infusion

^d 1.5 hours (±10 minutes) after the start of third plamotamab infusion

^e 24 hours (±2 hours) after the start of the second plamotamab infusion

^f 48 hours (±4 hours) after the start of the 1st plamotamab infusion

^g Cytokine assessment is optional at these timepoints

^h Required only at Cycle 4 Day 1

Note: Predose pPK and ECG: can obtain up to 2 hours prior to the start of the infusion and can be -5 minutes before or +15 minutes after the end of infusion.

In addition to timepoints from Table 10, cytokines should also be drawn if there is clinical suspicion of CRS at any time and repeated 4 hours later.

In the event of a subject overdose, an unscheduled PK sample should be collected and sent to the designated central lab, if requested by the Medical Monitor.

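### The ADA samples requested after a Grade 3 or 4 CRS event are waived by a condition about cytokine monitoring, so post-onset ADA is lost on 8 of the 10 early plamotamab dosing days

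*Protocol*

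**What the plan says.** The Grade 3 and 4 list in Protocol section 4.6.1.6 has two consecutive sampling bullets.

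- Cytokines: "Obtain an unscheduled blood sample for cytokine analysis during the event and approximately 4 hours later, unless scheduled cytokine monitoring is already in progress" that day.
- ADA: "Obtain an unscheduled sample for anti-drug antibodies (ADA) testing as close to the onset of the event as possible", again at resolution, and about 28 days "following the event, unless scheduled cytokine monitoring is already in progress on the same visit day".

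The same exception closes the cytokine instructions for Grades 1 and 2 in that section and for neurotoxicity in section 4.6.1.7. The ADA bullet is the only place where it governs a different assay.

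The routine schedule is in Table 10 of section 5, titled "Sampling for Plamotamab Anti-Drug Antibodies, Cytokines, PK, and ECGs, and Rituximab Levels". These samples "are performed for subjects in Part 1 and subjects randomized to Arm A in Part 2". Predose samples are taken before the tafasitamab infusion on days when both antibodies are given. The SAP does not address this rule.

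**The concern.** The exception makes sense for cytokines, because a scheduled cytokine draw replaces an unscheduled one. It does not carry over to ADA. Nothing in the Protocol says that serum drawn for cytokines will be tested for ADA; section 8.1 keeps leftover serum for additional biomarker testing.

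The two schedules also differ. Cytokines are dense in Cycles 1 to 3, and plamotamab ADA is sparse and always predose on dosing days. A site following the text as written would therefore skip the antibody sample that the same sentence requests, mostly in the early cycles.

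What is at stake is antibody status measured at the time of a severe reaction. Sections 4.6.1.3 and 4.6.2 separate CRS from allergic and infusion-related reactions while noting shared manifestations, and section 4.6.1.6 adds that "Subjects with Grade 3 CRS or infusion reaction may be rechallenged once resolved". Severe events should be few, and a sample not drawn at the event cannot be recovered later.

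**Working it through.** The Protocol gives no figure to reproduce. The check applies the waiver to each plamotamab dosing day in Cycles 1 to 3.

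**Inputs**
- Dosing days (Table 9): C1 Days 1, 8, 15, 22; C2 Days 1, 8, 15, 22; C3 Days 1, 15. Total 4 + 4 + 2 = 10.
- Scheduled cytokines (Table 10): C1D1, C1D8, C1D15, C1D22, C2D1, C2D15, C3D1, C3D15, with predose, 7-hour and 24-hour draws (the 7-hour draw is optional on C2D15, C3D1 and C3D15). Total 8; none from Cycle 4.
- Scheduled plamotamab ADA (Table 10): predose on C1D1, C2D1, C3D1 and Day 1 of even cycles from Cycle 4, then end of treatment and 30 days later.

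**Day by day.** Cycles are 28 days, so onset day + 28 is the same day of the next cycle for a subject still on schedule.

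| Onset day | Cytokines | ADA scheduled | Onset ADA waived | Day + 28 | Cytokines then | ADA scheduled then |
|---|---|---|---|---|---|---|
| C1D1 | yes | predose | yes | C2D1 | yes | predose |
| C1D8 | yes | none | yes | C2D8 | no | none |
| C1D15 | yes | none | yes | C2D15 | yes | none |
| C1D22 | yes | none | yes | C2D22 | no | none |
| C2D1 | yes | predose | yes | C3D1 | yes | predose |
| C2D8 | no | none | no | C3D8 | no | none |
| C2D15 | yes | none | yes | C3D15 | yes | none |
| C2D22 | no | none | no | C3D22 | no | none |
| C3D1 | yes | predose | yes | C4D1 | no | predose |
| C3D15 | yes | none | yes | C4D15 | no | none |

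**Reading 1: the exception covers all three samples**
- Onset sample waived: 8 of 10 days, and 4 of 4 in Cycle 1.
- Of those 8 days, 3 have a scheduled plamotamab ADA, all predose; 8 − 3 = 5 have none.
- Scheduled ADA after onset on the same day: 0 of 8.
- A resolution sample is waived if the event resolves on a cytokine day, including the 24-hour draw (C1D9, for example). Otherwise it survives.

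**Reading 2: the exception covers only the 28-day sample**
- The 28-day point falls on a cytokine day for 4 of 10 onset days: C1D1, C1D15, C2D1, C2D15.
- C2D1 and C3D1 carry a scheduled ADA, so a substitute exists for 2 of the 4. For C1D15 and C2D15 there is none: 4 − 2 = 2 of 10.

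**Schedule discrepancy.** Section 7.1.1 states two-weekly plamotamab from Cycle 2, while Table 9 and the Cycle 2 column of Table 12 show weekly dosing. Under the section 7.1.1 text, C2D8 and C2D22 drop out and the onset count becomes 8 of 8. The main count here follows Table 9.

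**How many subjects.** Section 2.4.1 reports Grade 3 or higher CRS in 4 of 80 Phase 1 NHL subjects (5%), all at the first infusion. The flat-dose cohort of 14 had none (sections 2.4.2 and 2.4.3). As an assumption, applying 0% to 5% to the planned plamotamab recipients, 40 in Part 1 plus 200 / 2 = 100 in Arm A, gives 0 to 140 × 0.05 = 7 subjects. The Protocol gives no such rate for the triple combination.

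**The case against.** The strongest case on the other side has five parts.

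- **The expected severe events are the least affected.** Phase 1 Grade 3 or higher CRS came with the first infusion, and section 4.6.1 expects CRS mainly after the first dose. A C1D1 reaction has a predose ADA that day and another at C2D1, 28 days later. This stands as a limit on size. The predose sample still precedes the reaction, so the onset sample is not replaced.
- **No planned analysis depends on these samples.** Immunogenicity is exploratory (sections 3.3 and 4.2.3), section 11.11 reports incidence and titer by collection time point, and the Part 1 endpoint is CRS and TEAE incidence. No ADA-by-reaction analysis is planned. This stands.
- **The exception may cover only the 28-day sample.** The grammar allows it. The identical clause in the cytokine bullet, which applies to the whole bullet, favours the wider reading. The narrower one still leaves the C1D15 and C2D15 gaps.
- **The scope is uncertain.** The list is a CRS guideline, section 4.6.1.4 offers it where local standards are absent or incomplete, and the bullet says ADA without naming the antibody. All of this is fair. Reading it as tafasitamab ADA does not help: Table 11 has that predose on C2D1 and C3D1 but on no Cycle 1 dosing day.
- **It looks like carried-over wording.** Probably so. A site following it would still omit a requested sample, and no other section corrects it.

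A reader might infer that ADA could not be related to severe reactions at all. The documents do not support that. Scheduled ADA on C1D1, C2D1, C3D1, even cycles from Cycle 4, end of treatment and 30 days later still gives subject-level status before and after an event, if the subject attends.

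**Conclusion.** The waiver is tied to the wrong assay and should be corrected. On the natural reading it removes the onset ADA sample on 8 of the 10 plamotamab dosing days in Cycles 1 to 3, with no scheduled post-onset sample on any of the 8. On the narrow reading it removes the 28-day sample without a substitute for reactions on 2 of the 10 days.

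The consequence is small. It concerns event-timed exploratory data in perhaps 0 to 7 subjects under the assumption above, and it leaves the primary and key secondary analyses untouched. The waiver does not apply on Days −8 and −4, on C2D8 or C2D22, from Cycle 4 on, or in Arm B, because no cytokines are scheduled there. Resolution and 28-day samples are judged on their own days and often survive, so it would be wrong to infer that the whole ADA series is dropped. Nor do the documents give a day-by-day distribution of Grade 3 or 4 infusion reactions, so the share of actual reactions affected cannot be stated.

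The counts rest on Table 9 for dosing and Table 10 for sampling. The 28-day results also assume that the subject remains on the plamotamab schedule after the event. The SAP (sections 1 and 4.1) records early termination with 3 subjects enrolled and listings only, so the point matters for the plan as designed and for any reuse of the text.

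**What to change.** In the Grade 3 and 4 ADA bullet of section 4.6.1.6, replace the condition with: *unless an ADA sample has already been drawn after onset of the event on the same day*. Add that a scheduled ADA sample falling within the visit window may stand in for the 28-day sample. It would help to name the antibody or antibodies to be tested.

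Merely changing the condition from scheduled cytokine monitoring to scheduled ADA sampling is not enough. It would still waive the onset sample on C1D1, C2D1 and C3D1 (3 of 10 days), where the scheduled ADA is predose.

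The cost is one sentence in an amendment and a few extra serum tubes in the subjects with Grade 3 or 4 events. Dosing and clinical management are unchanged.

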4.6.1.7. Neurotoxicity

In addition to CRS, another toxicity observed after CAR-T cell therapy and CD3 bispecific antibodies is neurotoxicity. Immune effector cell-associated neurotoxicity syndrome (ICANS) may manifest as delirium, encephalopathy, aphasia, lethargy, difficulty concentrating, agitation, tremor, seizures, and, rarely, cerebral edema (Lee, 2019). Neurotoxicity was previously considered in aggregate with CRS, but is now treated separately, due to its timing and response to treatment.

Neurologic symptoms may occur during or after CRS symptoms, but rarely precede CRS symptoms. The earliest manifestations of ICANS are tremor, dysgraphia, mild difficulty with expressive speech (especially in naming objects), impaired attention, apraxia, and mild lethargy. Headache is a nonspecific symptom, frequently occurring during fever or after chemotherapy in patients without other neurologic dysfunction. Thus, headache alone is not a useful marker of ICANS. Expressive aphasia, on the other hand, appears to be a very specific symptom of ICANS (Lee, 2019).

A consensus grading scheme, which is a slightly modified version of the CARTOX-10 screening tool, which incorporates key elements of the mini-mental state examination, the immune effector cell-associated encephalopathy (ICE) score, will be used for the grading of ICANS (Table 5). It is important to note that the 10-point ICE screening tool is helpful for assessing subjects for encephalopathy; however, the grading of ICANS requires assessment of the 10-point ICE score as well as evaluation of other neurologic domains, such as level of consciousness, motor symptoms, seizures, and signs of elevated intracranial pressure /cerebral edema, which may occur with or without encephalopathy. The ASTCT ICANS toxicity grading system is shown in Table 6. This grading scale will be used to assess neurotoxicity, rather than the CTCAE version 5.0.

Table 5: Immune Effector Cell-Associated Encephalopathy Scoring

ICE
Orientation: orientation to year, month, city, hospital: 4 points
Naming: ability to name 3 objects (eg, point to clock, pen, button): 3 points
Following commands: ability to follow simple commands (eg, “Show me 2 fingers” or “Close your eyes and stick out your tongue”): 1 point
Writing: ability to write a standard sentence (eg, “Our national bird is the bald eagle”): 1 point
Attention: ability to count backwards from 100 by 10: 1 point

ICANS = immune effector cell-associated neurotoxicity syndrome; ICE = Immune Effector Cell-Associated Encephalopathy (score).

Scoring: 10, no impairment;

7 – 9, Grade 1 ICANS;

3 – 6, Grade 2 ICANS;

0 – 2, Grade 3 ICANS;

0 due to patient unarousable and unable to perform ICE assessment, Grade 4 ICANS ([Lee, 2019](#)).

Table 6: American Society for Transplantation and Cellular Therapy Immune Effector Cell-Associated Neurotoxicity Syndrome Consensus Toxicity Grading for Adults

Neurotoxicity Domain	Grade 1	Grade 2	Grade 3	Grade 4
ICE score ^a	7–9	3–6	0–2	0 (patient is unarousable and unable to perform ICE)
Depressed level of consciousness ^b	Awakens spontaneously	Awakens to voice	Awakens only to tactile stimulus	Patient is unarousable or requires vigorous or repetitive tactile stimuli to arouse. Stupor or coma
Seizure	N/A	N/A	Any clinical seizure focal or generalized that resolves rapidly or nonconvulsive seizures on EEG that resolve with intervention	Life-threatening prolonged seizure (> 5 min); or Repetitive clinical or electrical seizures without return to baseline in between
Motor findings ^c	N/A	N/A	N/A	Deep focal motor weakness such as hemiparesis or paraparesis
Elevated ICP/cerebral edema	N/A	N/A	Focal/local edema on neuroimaging ^d	Diffuse cerebral edema on neuroimaging; decerebrate or decorticate posturing; or cranial nerve VI palsy; or papilledema; or Cushing’s triad

EEG = electroencephalogram; ICANS = immune effector cell-associated neurotoxicity syndrome; ICE = Immune Effector Cell-Associated Encephalopathy (score); ICP = intracranial pressure; N/A = not applicable; VI = sixth.

ICANS grade is determined by the most severe event (ICE score, level of consciousness, seizure, motor findings, raised ICP/cerebral edema) not attributable to any other cause; for example, a patient with an ICE score of 3 who has a generalized seizure is classified as grade 3 ICANS.

^a A patient with an ICE score of 0 may be classified as Grade 3 ICANS if awake with global aphasia, but a patient with an ICE score of 0 may be classified as Grade 4.

^b Depressed level of consciousness should be attributable to no other cause (eg, no sedating medication).

^c Tremors and myoclonus associated with immune effector cell therapies may be graded according to CTCAE v5.0, but they do not influence ICANS grading.

^d Intracranial hemorrhage with or without associated edema is not considered a neurotoxicity feature and is excluded from ICANS grading. It may be graded according to CTCAE v5.0 (Lee, 2019).

It has been speculated that high levels of IL-6 may directly mediate neurotoxicity in this situation (Lee [A], 2014). A human anti-IL-6 monoclonal antibody, tocilizumab, may reverse this

neurotoxicity, but it would not be expected to cross the blood brain barrier, and efficacy in this setting has not been confirmed. Therefore, it is suggested that corticosteroids be the primary therapy in this situation, and tocilizumab considered only if this proves ineffective.

Clinical management of neurotoxicity:

- Monitor subjects closely for signs and symptoms of these events (including the use of mental status and neurologic examinations).
- If neurotoxicity becomes evident, draw an unscheduled blood sample for cytokine analysis at that time, and again 4 hours later, unless scheduled cytokine monitoring is already in progress on the same visit day.
- If neurologic toxicity is Grade 4, discontinue plamotamab.
- For Grade 3 neurologic toxicity, withhold drug until the toxicity has recovered to \leq Grade 1 (mild) and has remained at \leq Grade 1 for at least 3 days before restarting therapy. Restart at 75% of the previous dose. Escalate back to full dose at the time of the next dose if \geq Grade 2 toxicity does not recur. If \geq Grade 2 toxicity reoccurs at 75% dose, or if $<$ Grade 2 toxicity takes more than 7 days to resolve, discontinue permanently. If Grade 3 neurologic toxicity persists for more than 7 days, permanently discontinue plamotamab.
- For severe neurologic symptoms, administer additional dexamethasone 10 mg intravenously and repeat every 12 hours if symptoms do not abate rapidly.
- For recurrent seizures, anticonvulsant therapy may be necessary.

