		
on the C1D1 dose, in which case 100% of the previous dose may be given.
 
 • For subsequent plamotamab infusions, if: 
 – Toxicity does not recur or recurs at a Grade 1 severity, escalate to full dose of plamotamab at the time of the next dose. – Toxicity recurs at a Grade 2 severity, maintain 75% dosing of plamotamab. – Toxicity recurs at \geq Grade 3 severity at any time or if a Grade 2 takes more than 10 days to resolve to \leq Grade 1, discontinue plamotamab permanently. • Lenalidomide is also modified if a \geq Grade 3 CRS event occurs: 
 – During the first 5 doses of plamotamab: Reduce current dose of lenalidomide by 10 mg (or to 5 mg if currently at 10 mg) for subsequent doses until C4D1, when lenalidomide may be increased back to the dose prior to CRS. If CRS recurs at \geq Grade 2 on subsequent reduced dose lenalidomide, permanently discontinue lenalidomide. – After the first 5 doses of plamotamab: Reduce lenalidomide by 10 mg (or to 5 mg if currently at 10 mg) for all subsequent doses. If CRS recurs at \geq Grade 2 on subsequent reduced dose lenalidomide, permanently discontinue lenalidomide. • Tafasitamab dose is not modified.
Myelosuppression	Platelet count of less than 50,000/ μ L	
 • Withhold plamotamab, tafasitamab, and lenalidomide and monitor CBC weekly until platelet count is 50,000/μL or higher. • Resume plamotamab and tafasitamab at the same dose and lenalidomide at a reduced dose. Refer to lenalidomide prescribing information for dosage modifications. • If recurrence, repeat drug withholding and lenalidomide reduction steps until minimal lenalidomide dose is reached per lenalidomide prescribing information. • If recurrence at minimal lenalidomide dose, repeat drug withholding step (first bullet above) then reduce the next scheduled plamotamab dose to 75% of the previous dose.

Adverse Reaction	Severity	Dosage Modification

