	
Neutrophil count of 1,000/μL or less for at least 7 days OR
 
Neutrophil count of 1,000/μL or less with an increase of body temperature to 100.4°F (38°C) or higher OR
 
Neutrophil count less than 500/μL
	
 • Withhold plamotamab, tafasitamab, and lenalidomide and monitor CBC weekly until neutrophil count is 1,000/μL or higher. • Resume plamotamab and tafasitamab at the same dose and lenalidomide at a reduced dose. Refer to lenalidomide prescribing information for dosage modifications. • If recurrence, repeat drug withholding (first bullet above) and lenalidomide reduction steps until minimal lenalidomide dose is reached per lenalidomide prescribing information. • If recurrence at 5 mg lenalidomide, repeat drug withholding steps then reduce the next scheduled plamotamab dose to 75% of the previous dose.
Febrile Neutropenia	Grade 3 (severe) & Grade 4 (life-threatening)	
 • Withhold plamotamab, tafasitamab, and lenalidomide and monitor CBC until neutrophil count is Grade \leq 1. • Once subject is afebrile, off antibiotics and neutrophil count is Grade \leq 1, resume all therapy at the same dose and schedule.
Neurotoxicity	Grade 3 (severe)	
 • Withhold plamotamab and manage signs and symptoms (see Section 4.6.1.7) until the toxicity has recovered to \leq Grade 1 (mild) and has remained at \leq Grade 1 for at least 3 days before restarting therapy. • Reduce next scheduled plamotamab dose to 75% of the previous dose. If \geq Grade 2 toxicity does not recur, escalate plamotamab to full dose in subsequent administrations. • If \geq Grade 2 toxicity recurs at 75% dose, or if $<$ Grade 2 toxicity takes more than 7 days to resolve, permanently discontinue plamotamab. • Tafasitamab and lenalidomide dosing is not modified.
	Grade 4 (life-threatening)	
 • Stop infusion immediately, if still infusing and permanently discontinue plamotamab.
AST, ALT, bilirubin, and alkaline phosphatase in the absence of CRS	Grade 3 (severe)	
 • Withhold plamotamab and manage signs and symptoms until the toxicity has recovered to \leq Grade 1 (mild) or baseline. • If a Grade 3 liver toxicity persists $>$ 14 days and/or 2 consecutive doses are missed and the toxicity cannot be attributed to another cause, permanently discontinue plamotamab. • Tafasitamab and lenalidomide dosing is not modified.

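### The restart, escalation and permanent-stop sentences for Grade 3 neurotoxicity do not fit together when Grade 1 toxicity persists, and the 7-day limit has no stated start, end grade or precedence

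*Protocol*

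**What the plan says.** Section 4.6.1.7 of the Protocol, under clinical management of neurotoxicity, gives four steps for a Grade 3 event.

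- Plamotamab is withheld until toxicity is at or below "Grade 1 for at least 3 days before restarting therapy".
- It then resumes at a lower level: "Restart at 75% of the previous dose".
- The dose goes back up: "Escalate back to full dose at the time of the next dose", on the single condition that toxicity of Grade 2 or higher has not come back.
- Plamotamab stops for good if Grade 2 or higher comes back at the 75% dose, or, in the second limb, "if $<$ Grade 2 toxicity takes more than 7 days to resolve, discontinue permanently".

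Table 8 in Section 4.7 repeats the scheme. If toxicity at or above "Grade 2 toxicity does not recur, escalate plamotamab to full dose in subsequent administrations". For toxicity below that grade the row reads "Grade 2 toxicity takes more than 7 days to resolve, permanently discontinue plamotamab", with the less-than sign immediately before those words. Since both places carry the same inequality signs, an error in reading the PDF is an unlikely explanation.

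**The concern.** Grade 1 toxicity is good enough for restarting and does not block return to full dose, but if it lasts it is also a reason to withdraw the drug permanently. A site with such a subject finds two different instructions in the same paragraph, and the other location repeats both.

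The choice affects only subjects who receive plamotamab (Part 1 and Part 2 Arm A). It would change their exposure and the count of treatment-emergent events leading to permanent plamotamab discontinuation, which Section 11.8 lists as an endpoint. It would also change the Part 1 safety evaluation that Section 4.1.1 uses to choose the Part 2 dose. For the subject, the difference is between a dose increase after a severe neurological event and loss of the investigational drug.

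**Working it through.** No power, alpha or event count is involved and the plan gives no figure to reproduce. The check sets the trigger conditions side by side and asks whether one subject can meet more than one of them.

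**Step 1: conditions, the same in Section 4.6.1.7 and Table 8**

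| Instruction | Stated condition | Met by unchanged Grade 1? |
|---|---|---|
| Restart at 75% | Grade 1 or lower, held at least 3 days | Yes. Clearance is not asked for and no upper limit on duration is set |
| Return to full dose | No recurrence of Grade 2 or higher | Yes |
| Permanent stop | Grade 2 or higher recurs at 75%, or toxicity below Grade 2 is unresolved after more than 7 days | Yes, through the second limb, once the clock passes 7 days |

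Elsewhere the sentences agree. Grade 1 that clears within 7 days leads only to escalation, and recurrence of Grade 2 or higher leads only to the stop. The overlap is confined to Grade 1 lasting more than 7 days.

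**Step 2: timing inputs.** Section 7.1.1 gives Cycle 1 dosing every 7 days (± 1 day) and every-2-week dosing later. Its text starts the 2-week interval at Cycle 2, while Table 12 shows weekly doses in Cycle 2 and the 2-week interval from Cycle 3; the check below needs only the two intervals. Call the day of the 75% restart day 0. If the clock starts then, more than 7 days is first true on day 8.

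**Step 3: assume the clock starts at restart.**
- Weekly dosing: the next dose falls on 7 ± 1, that is day 6, 7 or 8. On day 6 or 7 the full dose is due and the stop follows 8 − 6 = 2 days or 8 − 7 = 1 day later, for the same unchanged Grade 1. On day 8 the two coincide.
- Every-2-week dosing: the next dose falls on about day 14. The stop is due on day 8, which is 14 − 8 = 6 days earlier. By day 14 both conditions are met, but the stop came first.

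**Step 4: assume instead that the clock starts when toxicity falls to Grade 1 while the drug is withheld.**
- At least 3 days have passed by restart, so the stop falls due no later than 8 − 3 = 5 days after it. That is before the earliest next dose (day 6), so a subject with persistent Grade 1 could restart but would not reach full dose.
- If Grade 1 has already lasted 8 days before restart, the restart and stop conditions are both met at once.

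Under either start point the sentences conflict for persistent Grade 1; the start point decides only whether the stop collides with escalation or with restart.

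**The case against.** The best defence is that the paragraph states a rule and then its exception: escalate by default, but stop if either trigger occurs. A permanent stop leaves no next dose to escalate. On that reading a site is never ordered to do both, and a reader who infers that the protocol requires escalation and discontinuation together goes further than the text. That part of the defence stands. It does not repair the rule, because precedence is not written. Under weekly dosing the full dose can also still fall due on day 7 and the stop on day 8 with nothing having changed.

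It might be said that the 7-day limit is really about Grade 3. Section 4.6.1.7 has a separate sentence for Grade 3 persisting beyond 7 days, so that is not what this clause covers.

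Sites also have latitude. Section 4.7 lets investigators use standard practice for neurotoxicity, and Section 4.6.1.4 tells them to contact the Medical Monitor with questions on its management. Both make divergent handling less likely. Neither says which dose sentence governs, and Section 4.7 itself sends sites to Table 8 for detailed modifications by grade.

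A reader might also see a contradiction with the cytokine release syndrome row, which sets its limit with "if a Grade 2 takes more than 10 days to resolve" and names Grade 1 or lower as the target. Different toxicities may have different rules, so this is no contradiction. At most it suggests that the neurotoxicity clause was drafted less completely.

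**Conclusion.** The point holds as an internal inconsistency. For Grade 1 toxicity that lasts more than 7 days, the restart, escalation and permanent-stop sentences do not give one instruction, in either Section 4.6.1.7 or Table 8. The existence of the conflict rests on the text alone. The day counts rest on an assumed clock start and on residual Grade 1 that does not change.

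Two stronger inferences are not supported. A reader might conclude that under every-2-week dosing both rules are in force throughout days 8 to 14. Escalation attaches only to the next dose, so it is not in force between doses, and the day-8 figure itself depends on the clock starting at restart. A reader might also conclude that lingering Grade 2 has no time limit. Restart requires Grade 1 or lower held for at least 3 days, so Grade 2 after restart is a recurrence and triggers the stop. Grade 2 before restart keeps the drug withheld, and the general rule in Section 4.7 then applies: two consecutive missed doses may lead to discontinuation, and delays of more than 14 days and/or two consecutive doses need Medical Monitor approval. That limit is discretionary, but it exists.

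The size is small. The documents give no ICANS rate, so the number of affected subjects cannot be derived. SAP Sections 1, 4.1 and 7 report early termination with 3 subjects enrolled and listings only. What remains is a fault in the protocol text and in anything that re-uses it.

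**What to change.** The sponsor should reconcile the restart, escalation and permanent-stop sentences so that persistent Grade 1 toxicity leads to one instruction, and word Section 4.6.1.7 and the Table 8 Grade 3 neurotoxicity row identically. The sponsor's medical lead should state:

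- which grade the 7-day limit covers, and the grade to which toxicity must resolve;
- the event from which the 7 days are counted;
- which sentence takes precedence when more than one condition is met.

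No view is offered here on which clinical rule is right.

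The cost is a wording change in two places, with no extra subjects, visits or procedures. Because the study has ended, the change matters if the protocol is reopened or if its dose-modification text is carried into another plamotamab study.
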